- Age over 18 years;
- Disease duration ≤ 48 months;
- Score ≥ 2 at the item "swallowing" of the ALS Functional Rating Scale-Revised (ALSFRS-R);
- Score ≥ 1 at the item "walking" of the ALSFRS-R;
- Score ≥ 1 at the item "respiratory insufficiency" of the ALSFRS-R
- Signature of informed consent.

EXCLUSION CRITERIA for patients:

- Motor neuron diseases other than ALS;
- Diagnosis of dementia according to current clinical criteria;
- Severe head trauma in the past;
- Persons carrying static electrical stimulators (e.g. cardiac stimulators, nerve stimulators, auditory implants) that would not work or would be damaged by the magnetic field;
- Persons carrying special metallic foreign bodies (e.g. splinters, some prostheses, screws and nails) that could move if placed inside the magnetic field;
- People with a history of epilepsy or seizures;

CLINICA NEUROLOGICA - UNIVERSITA' DEGLI STUDI DI BRESCIA
UO Neurologia 2 - AZIENDA SOCIO SANITARIA TERRITORIALE degli SPEDALI CIVILI DI BRESCIA

Direttore: [name]

- History of ischemic stroke or hemorrhage;
- Severe comorbidity
- Given that the effects of TMS on the developing fetus are not known, pregnant women will be excluded from the study.

STUDY DESIGN:

This is a non-pharmacological, randomized double-blind controlled clinical trial. This study does not present sub studies. Patients will be randomized into two groups: each group will receive anodal bilateral motor cortex tDCS and cathodal spinal tDCS (real tDCS) or sham stimulation for 5 days/week for 2 weeks, in a 2:1 ratio respectively.

END POINTS:

The long-term effect of tDCS on clinical parameters (ALSFRS-R, ALSAQ-40, CBI, EQ-5D-5L, muscle strength assessed with the MRC scale in different muscle districts), and neurophysiological measures (SICI and ICF).

For efficacy analyses, the primary end point will be the defined as change from baseline in global MRC scores. Secondary end points will be defined as changes from baseline in the ALSFRS-R, ALSAQ-40, EQ-5D-5L, EQ-VAS, CBI and intracortical connectivity (SICI and ICF).

STATISTICAL PLAN:

Parametric analysis (t test) will be used to compare the demographic variables (e.g. age, duration of illness, education) of the various groups at the baseline. A p -value <0.05 will be considered significant.

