tDCS is a non-invasive, low cost and simple non-invasive brain stimulation method that is having an increasing diffusion and an increasingly numerous spectra of potential therapeutic applications such as, for example, post-stroke rehabilitation, depression and pain, which have already been established. Its effectiveness in modulating the excitability of the motor cortex in humans has been demonstrated (Nitsche et al., 2005). We therefore hypothesize that tDCS can have a positive effect on the clinical and quality of life scales, and restoration of neurophysiological parameters.

Literature data show that the application of the method according to the current safety guidelines (Iyer et al., 2005; Nitsche et al., 2003; Bikson et al., 2016) has little relevant side effects, among which mild tingling sensation during or after stimulation, moderate fatigue, mild itching sensation at the electrode sites, mild burning or pain, headache, nervousness, nausea, blistering at the electrode application points in rarer cases.

As for the TMS method, it is a non-invasive brain stimulation that allows the study of neurophysiological parameters that can provide information on the pathophysiological mechanisms involved in neurodegenerative diseases.

Literature data show that the application of the method according to the current safety guidelines has minor side effects: a certain number of subjects participating in TMS

CLINICA NEUROLOGICA - UNIVERSITA' DEGLI STUDI DI BRESCIA
UO Neurologia 2 - AZIENDA SOCIO SANITARIA TERRITORIALE degli SPEDALI CIVILI DI BRESCIA

Direttore: [name]

experiments (up to 20%) suffer from headaches or backaches, due to likely to an excessive muscle tension and a stiff position of the head and / or neck during TMS application. These effects are temporary and, in most cases, do not require any treatment.

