With the parameters that we will use in this study, epileptic seizures have never been reported (Rossi et al., 2009). If an epileptic seizure occurs, this would occur during TMS, not later. However, this is an extremely rare complication. To prevent this, all TMS sessions will be performed in the presence of a neurologist and by personnel trained to give first aid and to immediately recognize the first signs of epileptic seizures. In addition, all TMS sessions will be carried out within the Neurology Unit, equipped with all the emergency material needed to deal with epileptic seizures and to prevent any damage to the patient (emergency trolley organized according to the treatment of neurological emergencies, antiepileptic drugs).

The occurrence of an epileptic seizure during a TMS experiment does not imply that seizures will reoccur in the future, nor that you should start taking a therapy for the prevention of seizures, nor that we should modify an eventual therapy already underway due to a seizure. The very few cases of TMS-induced seizures described in the literature no longer had episodes later, nor did they report health problems attributable to the event.

Since the TMS produces a magnetic field, people carrying static electric stimulators (e.g. cardiac stimulators, nerve stimulators, auditory implants) that would not work or would be damaged by the magnetic field cannot participate in the study. Also excluded from the examination are the carriers of particular metallic foreign bodies (for splinters, some prostheses, screws and nails) that could move if placed inside the magnetic field. Because the effects of TMS on the developing fetus are not known, pregnant women cannot participate in the study.

ADVERSE EVENT DETECTION:

The Principal Investigator will promptly inform the Local Ethics Committee of the Brescia Hospital of any adverse event incurred during the study.

CLINICA NEUROLOGICA - UNIVERSITA' DEGLI STUDI DI BRESCIA
UO Neurologia 2 - AZIENDA SOCIO SANITARIA TERRITORIALE degli SPEDALI CIVILI DI BRESCIA

Direttore: [name]

REFERENCES

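### The protocol names expected tDCS side effects but plans no systematic collection of them at the ten sessions and no real-versus-sham summary of harms.

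*Combined protocol and SAP*

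**What the plan says.** ETHICAL CONSIDERATIONS (RISK-BENEFIT) names the expected effects of tDCS: "mild tingling sensation during or after stimulation, moderate fatigue, mild itching sensation at the electrode sites, mild burning or pain, headache, nervousness, nausea", and "blistering at the electrode application points in rarer cases". It gives no rates. For TMS, the same section says that some participants in TMS "experiments (up to 20%) suffer from headaches or backaches".

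ADVERSE EVENT DETECTION consists of one sentence: "The Principal Investigator will promptly inform the Local Ethics Committee of the Brescia Hospital of any adverse event incurred during the study". It does not define an adverse event, say how events are elicited, or provide for severity grading, a collection period or a summary by arm.

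Under END POINTS, the primary end point is the change in global MRC score. For the rest: "Secondary end points will be defined as changes from baseline in the ALSFRS-R, ALSAQ-40, EQ-5D-5L, EQ-VAS, CBI and intracortical connectivity (SICI and ICF". None of these is a safety or tolerability measure.

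Under PROCEDURES, the evaluations at T0, T1, T2 and T3 are clinical and neurophysiological. The question put to patients after the two weeks asks which arm they think they were in; it does not record symptoms. Under STATISTICAL PLAN, the real-versus-sham models cover clinical scores and TMS parameters only.

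The protocol does contain other safety measures, aimed at TMS: "To prevent this, all TMS sessions will be performed in the presence of a neurologist and by personnel trained to give first aid", in a unit "equipped with all the emergency material needed to deal with epileptic seizures and to prevent any damage to the patient". The exclusion criteria cover seizure history, implants, metal and pregnancy. These measures protect patients but generate no data on tDCS effects.

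**The concern.** The protocol argues a favourable balance of risk and benefit, but plans to measure only the benefit. A randomised sham arm is the best means of separating the effects of stimulation from background symptoms in a progressive disease, and the plan makes no use of it for harms.

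The listed effects are mostly mild and short-lived, the kind that patients often do not mention unless asked. If nobody asks at the sessions, the information cannot be recovered later. The plan also expects notable and possibly unbalanced drop-out. Without a tolerability record it would be hard to tell whether a withdrawal reflects intolerance or disease progression.

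**Working it through.** The plan states no figure for harms, so there is none to reproduce. The check has two parts.

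**1. Coverage of the named effects**

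| Place in the protocol | What it covers | tDCS tolerability? |
|---|---|---|
| END POINTS | MRC, ALSFRS-R, ALSAQ-40, EQ-5D-5L, EQ-VAS, CBI, SICI, ICF | No |
| PROCEDURES, T0 to T3 | Clinical scales and TMS | No |
| PROCEDURES, end of treatment | Guess of allocation | No |
| STATISTICAL PLAN | Models for clinical scores and TMS parameters | No |
| ADVERSE EVENT DETECTION | Notification of the ethics committee | Only if an event comes to notice |

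**2. What unsolicited reporting could miss**

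Inputs from the documents: 30 patients (STATISTICAL PLAN); 2:1 real to sham and 5 days a week for 2 weeks (STUDY DESIGN). Assuming the ratio is met exactly, with no drop-out and full attendance:

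- Patients: 30 × 2/3 = 20 real, 30 × 1/3 = 10 sham.
- Sessions: 5 × 2 = 10 each, so 200 real and 100 sham.

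Let p be the true proportion of real-arm patients with an effect such as a skin lesion, and c the share of cases that get reported. The chance that no case is recorded among 20 patients is (1 − p·c)^20. The documents give neither p nor c, so both are assumptions. Full capture (c = 1) stands for solicited checks.

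| p | c = 1 | c = 0.75 | c = 0.5 | c = 0.25 |
|---|---|---|---|---|
| 10% | 0.90^20 = 12% | 0.925^20 = 21% | 0.95^20 = 36% | 0.975^20 = 60% |
| 2% | 0.98^20 = 67% | 0.985^20 = 74% | 0.99^20 = 82% | 0.995^20 = 90% |
| 1% | 0.99^20 = 82% | 0.9925^20 = 86% | 0.995^20 = 90% | 0.9975^20 = 95% |

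At half capture, the chance of missing every case rises by about 24 points at a rate of 10%, 15 points at 2% and 9 points at 1%.

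**What better collection could and could not show.** With zero events, the exact one-sided 95% upper limit is 1 − 0.05^(1/n):

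- 20 real patients: 1 − 0.05^(1/20) = 13.9%.
- 10 sham patients: 1 − 0.05^(1/10) = 25.9%.

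These limits are valid only if every patient was asked. For a formal comparison of 20 with 10 patients, the power of a two-sided Fisher test at 0.05 is 10% for assumed rates of 10% (sham) and 30% (real), 54% for 10% and 50%, and 81% for 10% and 65%. Only very large differences would be detected.

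**The case against.** The strongest reply has four parts.

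**Safety is not neglected.** A reader might infer that notification is the protocol's only safety procedure. It is not: there are TMS precautions and exclusions, and a contact impedance limit for all tDCS sessions. The point is confined to recording adverse events and summarising tDCS effects.

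**A comparison remains possible.** The notification duty covers any adverse event, and each event belongs to a randomised patient, so reports could be split by arm after unblinding. A reader who concluded that no comparison could be made would go too far. What stands is that none is planned, and that it would rest on reports whose elicitation and grading are unspecified. Staff who place electrodes ten times may well notice a visible lesion, so capture of skin effects could be better than half.

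**TMS does not bias the contrast.** Both arms have the same TMS schedule, so its headaches and backaches should fall alike in each. With an independent 20% background in both arms, the risk difference is only scaled by 1 − 0.20 = 0.80. Attribution in the individual patient suffers; the randomised comparison is diluted, not distorted.

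**Asking has a price.** Sham current ramps down after 5 seconds, while real stimulation runs for 20 minutes. Questions about tingling and a look at the skin could therefore hint at allocation, and the primary end point is manual muscle testing, which depends on patient effort and rater judgement. This is a fair objection, and the checklist has to be designed around it.

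A reader might also infer, from the titles of the modelling papers cited for the cortico-spinal technique, that this trial is a main source of tolerability data for the montage. The documents do not support that. Other sources are cited for safety, a pilot study is mentioned, and the text does not show what tolerability data exist elsewhere.

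**Conclusion.** The point holds as a gap in data collection and reporting: the named tDCS effects are not systematically sought, and no by-arm summary is planned. No efficacy estimate or test is affected. The change is still worth making, because it is cheap and the data must be gathered at the sessions or not at all.

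The size depends on assumptions. The rates of 1% to 10% and the capture shares are illustrations. The protocol calls blistering rarer, so the lower rates, where the gain is smaller, may be nearer the mark for that effect. The 20 and 10 assume an exact 2:1 split without drop-out. That reports would be unsolicited follows from the protocol's silence on elicitation; actual practice at the site could be better. Even with full collection the result would be descriptive.

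**What to change.** Add a descriptive secondary tolerability end point:

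- After each of the ten sessions, in both arms, staff already present complete the same neutrally worded checklist of the effects listed under ETHICAL CONSIDERATIONS (present or absent, severity) and look at the electrode sites.
- At T1, T2 and T3, ask about adverse events before TMS starts, and log events during or after TMS separately.
- Keep the checklist results from the MRC, clinical-scale and TMS assessors until the data are locked.
- Report the number and proportion of patients with each event by arm, with exact confidence intervals and no claim from a significance test.
- Keep the ethics committee notification.

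The cost is a one-page form, an estimated one to two minutes per session, some data entry and one table. More minor events will be recorded. The risk to blinding is real but manageable with identical wording in both arms and separation from the outcome assessors. No extra visit is needed, and stimulation is unchanged.
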